7.3.2 Performing a Quality Control Test with the A1C+Now Monitor

Each A1CNow+ Monitor performs over 50 internal chemical and electronic quality control checks, including potential hardware and software errors (e.g. cartridge alignment, programming), and potential reagent strip errors (e.g. insufficient sample volume, invalid calculations). The Monitor has been programmed to report an error code if these quality checks are not passed.

Control testing solutions are not included with testing kits. When ordering new test kits, you must order and purchase both the high and low control solutions in addition to the kits.

Follow manufacturer instructions for properly conducting a QC test with the A1C+Now System. Record the QC result and any comments on the A1C+Now Quality Control Log (**Appendix R**). All QC logs should be saved and stored with other project documents. When a monitor fails a QC test, refer to the user manual for troubleshooting steps and then perform a second QC test. If after troubleshooting, a monitor still does not pass a QC test, replace the monitor.

Quality control testing should be performed at the following times:

- With each new shipment
- With each new lot
- With each new operator (conduct QC test before a newly trained staff begins using monitor with clients)
- Whenever problems (storage, operator, instrument, or other) are identified
- To ensure that storage conditions have not affected the product, run a control sample before running a patient sample if the test kit has been stored for more than a month and it has been at least a month since the last control testing

The measured value should be within the acceptable limits stated for the control material (refer to specific instructions and limit information included with control testing solutions). If the results obtained are outside the acceptable limit, please review the procedure and re-test the control material. If the measured value continues to fall outside the acceptable limit, please refrain from analyzing additional patient samples and contact Customer Service ([name]).

Good laboratory practices include a complete quality control program. This entails proper sample collection and handling practices, ongoing training of testing personnel, ongoing evaluation of control results, proper storage of test kits, etc. A permanent record of control results should be retained see A1C+Now Quality Control Log in **Appendix R**).

7.5 Regulatory requirements for testing

Conducting community-based screening and testing programs requires that organizations comply with a number of federal, state, and local regulations. FANO FAITH-DM project staff will provide technical assistance to food bank sites to support the sites in applying for and maintaining all required certifications in order to conduct testing. Food bank sites are ultimately responsible for ensuring that their organization is in compliance, and that any screening program is successfully meeting all regulatory requirements for the duration of the program. Sites cannot conduct any testing, screening, or monitoring until all regulatory requirements are met and maintained.

Regulatory requirements for conducting community-based screening and testing programs include the following:

7.5.1 CLIA Certificate of Waiver

Both of the devices we will use for testing (GE100 Blood Glucose Monitor, A1C+Now Monitor) are CLIA-waived devices. The Clinical Laboratory Improvement Amendments of 1988 (CLIA) program is managed by Centers for Medicare and Medicaid Services (CMS), and implemented through state CLIA offices. All project sites need to apply for CLIA certificates of waiver for use of these testing devices through their state offices, following the state-specific processes and forms. Funding is included in the food bank grants to cover all state and federal fees associated with obtaining and maintaining a CLIA certificate of waiver.

7.5.2 Medical Waste Permitting

For the FAITH-DM study, the only medical waste that will be generated by the sites are sharps (single-use lancet devices). We anticipate that each site will generate under 10 pounds of sharps medical waste each month. Regulations addressing the use, storage, transport, and treatment of sharps and sharps containers vary by state. In Texas, generators who generate 50 pounds or less per month of medical waste are exempted from permit, registration, and notification requirements. Both California and Michigan require organizations apply for and maintain permits to transfer and store medical waste that includes sharps, regardless of the quantity generated monthly.

- To meet state requirements for Small Quantity Medical Waste generators and for Limited Quantity Hauling Exemptions, sites will submit applications and associated fees to their appropriate state or county offices.
- Sites will submit a “Medical Waste Management Plan” along with their application, and use a Medical Waste Tracking Log (**Appendix S**) to document waste management.

- All sites will utilize a USPS-approved medical waste mail back service (Sharps Compliance, Inc.: <http://www.sharpsinc.com/>) for purchase of sharps containers, shipping, tracking, and treatment of medical waste generated during screening activities.

7.5.3 Additional Screening Requirements

Sites will submit applications and program materials as required to address any additional local regulations relative to conducting screening and testing in the community setting.

- Non-Diagnostic General Health Assessment (NDGHA) application
 - Sites located in California need to complete and submit a NDGHA application annually to their local county health department in order to meet state screening requirements
 - The application must be submitted at least 30 days prior to any screening activities taking place, and must include all required information and documentation relative to program protocols, staff credentials, and screening locations, dates, and times
 - Sites must also include with their application materials the names and credentials (phlebotomist, RN, MA, PA, MD, etc.) of all staff that will be conducting screening.

7.6 Survey Administration

This section of the MOP covers instructions for the administration of surveys used in the course of this study. Surveys are administered by trained FAITH-DM research staff to consented food bank clients in the participant’s preferred language. All surveys will be administered via the CASIC data collection software on a laptop provided by University of California San Francisco.

This study includes a baseline survey and two follow-up surveys. All participants will complete the same Baseline Survey (**Appendix U**). Intervention group participants will complete the Follow-Up Survey Intervention (**Appendix V1**) at T6. Control group participants will complete the Follow-Up Survey Control Survey (**Appendix V2**) at T6. As a result of study extension funding, both groups will also complete surveys at T12. The T12 INT survey (**Appendix W1**) is identical to the T6 INT survey, but does not include any satisfaction items. The T12 CONT survey (**Appendix W2**) is identical to the T6 INT follow-up survey.

The timing for completing the T6 and T12 follow-up surveys is outlined below and uses the same time windows for follow-up HbA1c testing.

SURVEY VERSION	GROUP	TIMING*
Baseline	All Participants	T0
T6 Follow-up (INT)	Intervention Group	T6 (5 – 7 months [6±1])
T6 Follow-up (CONT)	Control Group	T6 (5 – 7 months [6±1])
T12 Follow-up (INT)	Intervention Group	T12 (11 – 13 months [±1])**

T12 Follow-up (CONT)	Control Group	T12 (11 – 13 months [12±1])**
----------------------	---------------	-------------------------------

* 1 month = 30 DAYS ALWAYS

** Alternatively, T12 survey windows can be manually calculated as 5-7 months **after** the completion date of a participant’s T6 follow-up activities. This revision will accommodate participants who complete their T6 activities at month 5 (earliest part of the window) and maintain a 5-7 month separation between the T6 and T12 follow-up activities.

If a participant does not complete their follow-up survey at T6 or T12, study staff can still complete it with the participant when they are next seen at a pantry or study activity. Participant surveys can also be completed over the phone if necessary.

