If a participant does not complete their follow-up HbA1c test at T6 or T12, study staff can still complete an HbA1c test with the participant when they are next seen at a pantry or study activity.

Any HbA1c test completed beyond the follow-up windows should be entered in the MS Access database as an “extra” test.

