3.4.2 Brief 1-on-1 interactions

1-on-1 interactions are offered to participants in the intervention group (T0-T6) and to control group participants (T6-T12).

In order to reinforce DSME messages participants receive in the group class series or through the bi-monthly passive education materials, health educators and food pantry staff will conduct brief 1-on-1 interactions and check-ins with participants over the course of the intervention. These interactions will take place during food distributions when participants pick up their bi-monthly food boxes.

These interactions will assist participants in acquiring and reinforcing diabetes self-care knowledge and developing and strengthening diabetes self-management skills by providing a support structure for participants. The interactions are opportunities for study staff to listen to participant feedback, challenges, and successes, as well as to provide participants with information on other existing community-based resources. In order to meet this obligation, study staff should be accessible and open to questions and informally check in with participants during food box distributions. Being proactive, friendly, and enthusiastic is critical to the success of this informal intervention component.

Health educators at sites will utilize materials from the diabetes education curriculum to interact with participants and respond to comments and questions relative to the AADE7™ Self-Care Behaviors. Sample questions and prompts to initiate interactions with participants include:

- What have you been working on to help take care of your diabetes?
- What challenges have you had with your diabetes?
- How do you like the diabetes food packages included in the FAITH-DM project? What changes would you like to see with the food packages?
- What questions do you or your family have about taking care of your diabetes?
- What challenges have you had with keeping to your plan to eat healthy?
 - Educators can utilize existing food bank nutrition education resources and expertise
 - Focus on Healthy Eating messages (MyPlate, label reading, portion control, “rethink your drink”, etc.)
- Review bi-monthly passive diabetes education materials
 - Highlight any local resources that relate to current topics

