3.6 Length and time windows for intervention

For participants in the intervention group, access to the food package and DSME intervention components is only available during their 6-month intervention window (T0-T6). Intervention group participants should no longer have access to these elements after they reach their T6 time point in the study (they will have access to referrals for care, if needed, at T6 and T12, and have access to HbA1c testing and monitoring at T6 and again at T12).

For participants in the control group, access to the food package and the modified DSME intervention components is also only available during their 6-month intervention window (T6-T12). Control group participants should not have access to intervention components prior to T6, nor should they continue receiving any intervention components after T12. Control group participants will have access to referrals for care, if needed, at T6 and T12, and have access to HbA1c testing and monitoring at T6, T9, and again at T12 per existing study protocols.

Site adherence to these time windows will help achieve and maintain fidelity to the original study design. While sites may need to make minor, reasonable accommodations for individual participants (e.g., provision of a maximum of 2 food packages to be picked up within 1 month post T6 follow-up activities for intervention group participants), any deviation from these protocols should be logged in the MS Access database for the participant, and site staff should complete and submit a Protocol Deviation (**Appendix F**) form.

Any food bank services (e.g., food packages, education, support, referrals) provided or conducted after T12 activities for any study participant will be at the discretion of the food bank as these clients will no longer be enrolled in the study as active study participants.

4 Recruitment and Retention Plan

In order to meet recruitment targets, we will:

- Monitor recruitment and intervene quickly to change recruitment techniques that are proving unsuccessful; discuss on monthly calls
- Identify barriers to recruitment
- Use multiple recruitment strategies depending on the needs of each food bank or food pantry (see **Appendix AJ** for a sample recruitment flyer to post at pantry sites)
- If we are not meeting recruitment goals, we can employ additional outreach strategies such as English and Spanish language flyers and advertisements

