7.6.2 Completing surveys when participant needs to leave

At times, a participant may need to leave before administration of a survey is complete. If the participant completed approximately less than half the survey, staff should inform the participant that they will need to restart the survey and complete it at a future date.

Instructions for when a client does not start a survey or completes less than half:

- If possible, schedule a day and time to complete the survey within the next two weeks
- Verify the participant's contact information, and the information for their additional contacts (participant, friend, family member) in order to place reminder calls
- Remind client of the program benefits / incentive available once survey is completed
- Save participant ID# used to enter baseline data into ACCESS database and to start CASIC survey
 - Do NOT open the randomization envelope; do NOT assign client to a study group
- In the event the participant does not start or complete the survey within the two week period:
 - The client will be considered lost to follow-up; add note to ACCESS
 - Notify [name] that client did not start/complete survey and was not randomized
 - Do not reuse the participant ID# and destroy the randomization envelope
 - If the participant was completing a follow-up survey, notify [name] that the survey was not completed within the two-week window

Instructions for when a participant completes approximately half of the survey or more:

- Site staff can save the survey and attempt to finish the remainder with the client within two weeks
- If completing a baseline survey, open the randomization envelope with the participant for group assignment before the participant leaves the site
 - If randomized to the intervention group, provide participant with resources and first food package per study protocols
 - If randomized to the control group, provide participant with 1st incentive (\$15 gift card) and have participant sign for receipt of the gift card
- If completing a follow-up survey, provide participant with the correct incentive and have participant sign for receipt of the gift card
- Verify the participant's contact information, and the information for their additional contacts (participant, friend, family member) in order to place reminder calls
- If possible, schedule a day and time to complete the survey within the next two weeks, either in person or over the phone

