- Month 5, Week 2
 - Participant receives bi-monthly food box, passive education materials, and 1-on-1 education from food bank staff
- Month 6, Week 1 = T6
 - Participant completes 6-month HbA1c test with study staff
 - Participant completes T6 survey with study staff (CASIC)
 - Participant receives \$30 gift card for completion of survey
 - Participant receives final bi-monthly food box, passive education materials, and 1-on-1 education from food bank staff
 - Participant attends monthly group drop-in diabetes education class
- Month 12 = T12

- Participant completes 12-month HbA1c test with study staff
- Participant completes T12 INT survey with study staff (CASIC)
- Participant receives \$15 gift card for completion of survey
- Participant formally exits research study

Participants – Control Group

- Day 1 (Month 1, Week 1) = T0
 - Food bank client participates in diabetes screening (blood glucose and/or HbA1c testing) event at food pantry; study staff verifies that client meets eligibility requirements for study inclusion
 - Client agrees to participate in study and completes written consent form with study staff
 - Participant completes baseline survey with study staff (CASIC)
 - Participant randomly assigned to study control group by study staff
 - Participant receives \$15 gift card for survey completion
- Month 1, Week 1 – Month 6, Week 2
 - Participant attends regular food pantry distributions and receives normal services per food pantry guidelines (does NOT receive diabetes food packages or education)
- Month 7, Week 1 = T6
 - Participant completes HbA1c test with study staff
 - Participant completes final survey with study staff (CASIC)
 - Participant receives \$15 gift card for survey completion
 - Participant receives 1st bi-monthly food box, passive education materials, and 1-on-1 education from food bank staff
- Month 7, Week 2
 - Participant receives bi-monthly food box, passive education materials, and 1-on-1 education from food bank staff
- Month 8, Week 1
 - Participant receives bi-monthly food box, passive education materials, and 1-on-1 education from food bank staff
- Month 8, Week 2
 - Participant receives bi-monthly food box, passive education materials, and 1-on-1 education from food bank staff
- Month 9, Week 1
 - Participant receives bi-monthly food box, passive education materials, and 1-on-1 education from food bank staff
- Month 9, Week 2 = T9

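### A missed T6 survey has no latest date, so some control surveys may be taken after food boxes have begun and dilute the survey-based secondary outcomes

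*Combined protocol and SAP*

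**What the plan says.** **Survey timing.** Section 7.6 says the timing of the follow-up surveys "uses the same time windows for follow-up HbA1c testing", which for T6 means 5–7 months in both arms. If the survey is missed, "study staff can still complete it with the participant when they are next seen at a pantry or study activity". The section adds: "Participant surveys can also be completed over the phone if necessary". None of these routes carries a latest date.

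**Unfinished surveys.** Where at least about half has been done, Section 7.6.2 says: "Site staff can save the survey and attempt to finish the remainder with the client within two weeks". After two weeks the survey is noted as incomplete.

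**HbA1c, for contrast.** Section 3.1.4 also allows a missed test to be done at the next contact, but it goes on: "Any HbA1c test completed beyond the follow-up windows should be entered in the MS Access database as an" extra test. Surveys have no counterpart to this.

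**Control schedule.** In Section 9.1, T6 for controls is Month 7, Week 1. After the HbA1c test and the survey it lists: "Participant receives 1st bi-monthly food box, passive education materials, and 1-on-1 education from food bank staff". Boxes then continue twice monthly to T12, and Appendix E repeats this. On the 1-on-1 contacts, Section 3.4.2 says: "These interactions will take place during food distributions when participants pick up their bi-monthly food boxes".

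**Access rule.** Section 3.6 says: "Control group participants should not have access to intervention components prior to T6". The rule is tied to the T6 time point, not to completion of the T6 survey.

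**Analysis.** Section 13.4.4 fits an ANCOVA by assigned arm to all outcomes in Section 13.4.3. It has no term or rule for survey date or for control exposure. Section 13.4.2 speaks of 4–9 months between baseline and follow-up.

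**The concern.** In a waitlist design the control measurement is valid only while the control is still waiting. For surveys, the plan leaves the end of that period open. A control who misses the T6 survey can start boxes because the T6 time point has passed, and can answer the survey later. Those answers would be analysed as untreated.

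The outcomes at stake are the secondary ones in Section 13.4.3. Several of them (fruit and vegetable intake, food security, trade-offs between food and medication) are what the boxes aim to change. If the intervention works, treated-period answers in the control arm narrow the difference between arms. A null secondary result could then come partly from survey timing, and the analysis as planned could not show it.

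**Working it through.** The plan states no figure on this point, so there is none to reproduce. The check is a timeline, a reading of the rules side by side, and an illustration of size.

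**1. Timeline** (Sections 3.1.4 and 7.6 fix one month at 30 days)
- T6 window: 5 × 30 = day 150 to 7 × 30 = day 210.
- Month 7 starts on day 6 × 30 + 1 = 181.
- Control boxes on schedule: Month 7, Weeks 1 and 2, then twice monthly.

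A control whose boxes start on schedule could collect up to two before the window closes on day 210. Any control survey after day 210 falls inside the T6–T12 intervention period. The nine-month upper figure in Section 13.4.2 reaches day 9 × 30 = 270.

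**2. Does any rule prevent box before survey?**

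| Place | What it does | Does it close the gap? |
|---|---|---|
| 9.1, Appendix E | List survey before first box at control T6 | No. This is an order within one visit, not a condition |
| 3.6 | No components for controls before T6 | No. Tied to the time point |
| 7.6.2, half or more done | Two weeks to finish, then noted incomplete | Limits this route, but the two weeks can follow a first box |
| 7.6.2, not started or under half done | After two weeks a follow-up survey is notified | No. It does not say the survey is closed |
| Appendix F, code 13 | Logs visits outside the window | No stated effect on the analysis |
| 13.4.4 | ANCOVA by assigned arm | No rule on date or exposure |

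**3. Illustration of size**
Let δ be the true effect, f the share of control T6 surveys taken after exposure began, and c the share of δ those controls already show. Assume they are otherwise like the other controls.
- Control mean = μ + f·c·δ
- Intervention mean = μ + δ
- Observed difference = δ(1 − f·c)

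The documents give neither f nor c. Both are assumptions.

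| f | c = 0.25 | c = 0.5 | c = 1 |
|---|---|---|---|
| 0.05 | 1.25% | 2.5% | 5% |
| 0.10 | 2.5% | 5% | 10% |
| 0.20 | 5% | 10% | 20% |

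Entries are the shrinkage f·c. For surveys finished within two weeks of a first box, the low end of c is more plausible: only the remaining items are affected, after one or two of the 11 boxes. For surveys taken months later, c could be larger.

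**The case against.** **The next contact need not be a box pick-up.** This stands. Section 7.6 names pantry visits as well as study activities and allows the phone, and controls also use ordinary pantry distributions. A reader might infer that every late control survey is taken at a box visit, and so after treatment. The text does not support that. A control who missed T6 can be surveyed at the next visit before the first box, in the order already scheduled. What remains is that no route is dated and nothing requires that order.

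**Controls are already in place.** Partly right. Box pick-up dates are tracked (Section 3.5), out-of-window visits have a deviation code, and Section 7.6.2 asks for notification or a note after two weeks. These record the event. None says how the survey is analysed.

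**HbA1c is handled no better.** Also partly right. A reader might infer that late HbA1c values are excluded from analysis. Section 3.1.4 says only which field they go into, and Section 13.4 does not say how that field is used. Leaving late surveys out of the main T6 analysis is therefore a new rule, not a copy of an existing one.

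**The intervention arm is not immune.** Correct. Section 3.6 allows up to two packages in the month after T6, and a late intervention survey could also miss a benefit that has faded. A date rule should therefore cover both arms.

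**A power loss can be read off.** It cannot. A reader might apply a 10% shrinkage to the sample size calculation and report a fall from 90% to about 83%. That uses the HbA1c effect of 0.4, the HbA1c standard deviations and the correlation of 0.51. Section 13.4.3 claims power only for HbA1c, and no power is stated for any survey outcome.

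**Conclusion.** The gap is real and limited. Sections 7.6 and 7.6.2 permit a control T6 survey to be completed after boxes and education have begun, and neither the schedule, the access rule nor the analysis deals with it. If the intervention works, the control-arm effect is a bias toward no difference in the survey-based secondary outcomes.

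The documents show a possibility, not a frequency. They do not give the share of late surveys. The survey instruments are not in the text, and no recall periods are given for the outcomes in Section 13.4.3, so the response to one or two boxes cannot be judged. The 1.25–20% range rests entirely on the assumed 5–20% of surveys and quarter-to-full effect.

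The primary HbA1c comparison and its power are not affected by this point. It is worth correcting because the secondary outcomes carry much of the food-related interpretation and the correction is cheap.

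**What to change.** **Section 7.6 (conduct).** State that when a control is next seen with the T6 survey outstanding, the survey is done before the box is handed over at that visit. This is the order already listed in Section 9.1 and Appendix E.

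**Section 7.6 (storage, both arms).** Store a T6 survey completed after the 5–7 month window as a late, or extra, survey, in the way Section 3.1.4 stores late HbA1c tests. State that it is not used in the main T6 analysis.

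**Flag.** Keep control surveys completed inside the window, even if wholly or partly after the first box, but flag them by comparing the CASIC survey date with the Access box date. Dropping them would remove data from one arm only. Under Section 13.4.4 that loss might go unadjusted, because adjustment depends on a significant difference in attrition and multiple imputation is only to be explored. Confirm that CASIC keeps a completion date; the documents do not say so explicitly.

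**Section 13.4.4.** Prespecify two sensitivity analyses: one adding the late surveys from both arms, and one setting the flagged control surveys to missing with multiple imputation. Report late and flagged counts by arm, and reconcile the 4–9 months in Section 13.4.2 with the 5–7 month window.

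**Cost.** A few sentences in the manual, one derived flag, a few more missing T6 surveys in the main analysis and a little more analysis work.
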